492 physical activity. Subjects will be asked to wear the monitors from day 5 to day 23 (last day of
493 inpatient). The Actigraph is designed to be worn for about one week at a time so the monitors will be
494 changed twice on about day 15 and day 17.

495 **Day 6:** Participants will spend approximately 23 hours and 15 minutes in the respiratory chamber for
496 the assessment of energy metabolism during eucaloric conditions at an ambient temperature of 24°C,
497 which is maintained by an adjustable air conditioning system. The respiratory chamber is a
498 comfortable, air-tight room (10 feet x 8 feet x 7 feet, net volume ~20,000 liters) constructed as a large
499 open-circuit whole-room indirect calorimeter. It is furnished with a toilet, sink, bed, desk, chair, color
500 television, DVD player, and radio. Visual contact with the subject is possible through one of the
501 windows and verbal contact is possible via the telephone. An emergency call bell is within reach of
502 the bed and toilet. Food is provided into the chamber through an airtight interlock. Spontaneous
503 physical activity (SPA) is continuously monitored by a radar system based on the Doppler Effect. The
504 flow rate through the chamber and the CO₂ and O₂ concentrations of the out-flowing air are
505 continuously computed, and calculations of oxygen consumption, carbon dioxide production, RQ [57],
506 and SPA are made every minute. Volunteers will be asked to only engage in sedentary activities while
507 in this chamber. Breakfast will be given immediately before volunteers enter the chamber. Total food
508 intake for the day (four meals total) will be equivalent to 80% of the weight maintaining diet to
509 account for the restricted physical activity in the confined environment of the chamber.

510 Prior to entering the respiratory chamber, fasting blood will be collected for measurement of
511 insulin, glucagon, leptin, adiponectin, ghrelin, insulin-like growth factor 1 (IGF-1), active GLP-1, PP,
512 PYY, IL-6, free T3, free T4, TSH, FGF21, estradiol (women only) and progesterone (women only), beta-
513 hydroxybutyrate, lactate, pyruvate. A 24 hour urine specimen will be collected for measurement of
514 nitrogen, urinary catecholamines, and urinary free cortisol. Carbohydrate and fat oxidation rates will
515 also be calculated after accounting for protein oxidation, estimated from measurement of 24-h
516 urinary nitrogen excretion [58].

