517 During the approximately 23.25-h stay in the respiratory chamber, the subjects will complete a
518 Visual Analogue Scale (VAS) for measurement of appetite sensations, mood and body temperature
519 including hunger, anticipated food consumption, and desire to eat something fatty, salty, or sweet
520 [59, 60]. Subjects will complete this VAS at 3 time points: 1) prior to entering the chamber; 2) at
521 approximately 6:30 pm, prior to their evening snack; and, 3) immediately upon exiting the chamber.

522 We will use the CorTemp™ core body temperature monitoring system to assess body
523 temperature during this eucaloric feeding chamber. The system uses an ingestible, wireless sensor to
524 transmit a signal to a data recorder worn on the hip. The data recorder will be worn by volunteers for
525 the duration of the EE assessment to provide a continuous measurement of body temperature
526 change.

527 We will also ask the subjects to wear iButtons® to measure their skin temperature [61].
528 iButtons® are digital thermometers with a built-in real-time clock measuring 1.7 cm in circumference
529 and 0.6 cm in depth. They record more than 2000 consecutive temperature measurements to a 0.5°C
530 resolution which can then be downloaded to a computer. iButtons® are intended for monitoring of
531 the body temperature of humans and have been used in other studies to monitor peripheral skin

532 temperature [61, 62]. Because they are lightweight, they can be attached to the skin simply with tape.
533 Four iButtons will be used to measure distal skin temperature: two iButtons will be placed on the
534 wrist of both arms, and two iButtons will be placed at the ankles of both legs. Five iButtons will be
535 also used to measure proximal skin temperature: one cm below the navel (1°), near the left
536 paravertebral on the upper back (2°), two iButtons on the left and right supraclavicular fossa (3° and
537 4°), and one iButton near the right paravertebral at the lower back (5°).

538 **Day 7:** Upon exiting the respiratory chamber, the subjects will complete the VAS. Fasting blood will
539 then be collected for measurement of insulin, glucagon, leptin, adiponectin, ghrelin, IGF-1, active GLP-
540 1, PP, PYY, IL-6, free T3, free T4, TSH, FGF21, beta-hydroxybutyrate, lactate, pyruvate, to assess for
541 stability after a day of energy balance spent inside the metabolic chamber.

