567 provided during the vending machine assessment on the floor. Snacks, drinks, condiments and food
568 items will be stocked in a refrigerator within the respiratory chamber. A small microwave oven will be
569 available inside the chamber, just as in the vending room, for preparation of hot food items. The
570 participant will be asked to keep a record of the timing of all food consumption, and to place all waste
571 and leftover food in the air lock for weighing by the metabolic kitchen. Total energy intake will be
572 calculated as for day 7. A 24-h urine collection will again be done for nitrogen, cortisol and
573 catecholamines. Subjects will complete the VAS at 3 time points during the approximately 23.25 hours
574 inside the calorimeter. The results of this assessment will provide a measure of *ad libitum* food intake
575 inside the confined environment of the metabolic chamber at 24°C. This assessment will be used as

576 the baseline comparator for the energy intake assessment at 19°C when subjects will again be
577 confined within the metabolic chamber.

578 **Days 11, 12 and and 13:** After exiting the chamber, there will be a washout phase for any residual
579 effects of the excess food consumption expected to occur with *ad libitum* food intake to wane.
580 Subjects will be fed a weight maintaining diet.

581 ***Intervention Phase***

582 Procedures and interventions described on days 14-15 and 18 will be conducted in random order.
583 **Day 14:** Subjects will again spend approximately 23.25 hrs inside the respiratory chamber as above,
584 but this time the temperature will be set at 19°C. Prior to entering the respiratory chamber, fasting
585 blood will be collected for measurement of plasma glucose and insulin. The energy intake provided
586 during this chamber will equal the EE expended during the chamber assessment done on Day 6.

587 Standardized clothing, including shorts, a t-shirt and flip-flops will be provided for this 24-h EE
588 assessment. For sleep (from approximately 11 pm to 6 am), 3 blankets will be provided so that
589 volunteers can create their own microenvironment to achieve a level of comfort conducive to sleep. If
590 the subjects begin to shiver, they will be instructed to notify the nurse at the nurse's station and to
591 use the provided blankets until the shivering ceases.

592 The cold-induced thermogenesis (CIT, kcal/day) will be calculated as the difference between

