593 the 24-h EE at 19°C and 24-h EE at 24°C measured on Day 6. The CorTemp™ core body temperature
594 monitoring system will be used to assess changes in body temperature during this 24-h period.
595 Subjects will again be asked to wear 9 iButtons® to measure skin temperature changes during cool
596 temperature exposure. A 24-h urine collection will again be done for nitrogen, cortisol and
597 catecholamines. Subjects will complete the VAS at 3 time points during the approximately 23.25 hours
598 inside the calorimeter.

599 **Day 15:** Upon exiting the chamber, the subjects will complete the VAS. Fasting blood will be then
600 collected for measurement of insulin, glucagon, leptin, adiponectin, ghrelin, IGF-1, active GLP-1, PP,
601 PYY, IL-6, free T3, free T4, TSH, FGF21, estradiol and progesterone, beta-hydroxybutyrate, lactate,
602 pyruvate. Subjects will again spend 24 hrs using the vending machine paradigm, as above, for the
603 assessment of *ad libitum* food intake following the increased EE resulting from the cold-induced
604 thermogenesis during Day 14.

605 **Day 16 and 17:** This will be a wash-out period for any residual effects of the overeating expected to
606 occur during *ad libitum* food intake to wane [10]. Subjects will be fed a weight maintaining diet.

607 **Day 18:** Subjects will again reside for approximately 23.25 hrs in the respiratory chamber in a cool
608 environment (19°C), this time with access to food choices similar to those provided during the
609 assessment on Day 10. A 24-h urine collection will again be done for nitrogen, cortisol and
610 catecholamines. Subjects will complete the VAS at 3 time points during the approximately 23.25 hours
611 inside the calorimeter.

612 The amount of food intake on Day 18, as well as on Day 15, will help to determine the length
613 of time in which the cold-induced increase in EE might affect food intake, i.e. whether any EE-effect
614 on energy intake only occurs during cooler temperature exposure or whether the effect persists until
615 the following day. The amount of food intake consumed inside the metabolic chamber on Day 18 at
616 19° C will be compared to that obtained on Day 10 at 24°C in the same setting to evaluate the
617 difference in energy intake during the cool temperature exposure.

618 **Days 19 and 20:** This will be a washout period for any residual effects of the overeating expected to

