722 mass. In evaluating the relationship between altered EE by cool exposure/fasting and *ad libitum* food
723 intake, the concomitant RQ will also be included as further covariate in the multivariate model. Lastly,
724 sensitivity analyses accounting for the SPA inside the metabolic chamber will be done. Although we
725 anticipate that the wash-out period will remove any carry-over effect, potential order effects arising
726 from the cross-over design of the study will be assessed by including a dichotomous variable for the
727 sequence effect of interventions (e.g., 0 = “cold exposure & subsequent *ad libitum* food intake”; 1 =
728 cold & concomitant *ad libitum* food intake) in the multivariate models assessing the association
729 between change in EE and change in energy intake. Student t-tests will be also calculated to
730 determine if the change in EE or the change in energy intake differ between these two groups. If no
731 difference exists in the outcome variables between these 2 groups and the dichotomous variable is
732 not significant in the multivariate model, we will determine that no evidence for an order effect exists
733 and leave the dichotomous variable out of the final multivariate model. If there will be evidence of an
734 order effect, we will include the dichotomous variable in the multivariate model to ‘adjust’ for the
735 order effect.

736 To follow-up the regression analyses and assess potential causality linking EE to energy intake,
737 mediation analysis based on hierarchical multiple regression models as outlined in [66] will be used to
738 evaluate whether the effect of increased EE on energy intake is exerted through the influence of
739 mediators, including hormonal changes, RQ appetite sensations, behavioral and neurocognitive
740 scores. The Sobel test [67] will be used to test the significance of the mediation effect.

741 For all hormonal measures, the change in concentrations induced by the interventions will be
742 compared to the baseline fasting concentrations drawn prior to the energy balanced 24-h EE
743 assessment using paired t-tests for normally distributed data or the Wilcoxon nonparametric test for
744 skewed data. A sample size of 68 subjects will provide greater than 80% power with an alpha of 0.05
745 to detect a minimum mean expected decrease in fasting leptin, as a representative hormone, of
746 -1.8 ± 6.0 ng/mL as observed in prior studies measuring leptin concentrations during 24-h fasting [1].

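### Hormone changes after cold or fasting are tested against a pre-chamber sample (Day 6), although a better-matched post-chamber sample (Day 7) is already drawn

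*Combined protocol and SAP*

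**What the plan says.** **Comparator.** The hormone paragraph of Data Analysis states that changes induced by the interventions will be "compared to the baseline fasting concentrations drawn prior to the energy balanced 24-h EE" assessment, by paired t-test or Wilcoxon test. In the schedule this is Day 6: "Prior to entering the respiratory chamber, fasting blood will be collected for measurement of" the full panel.

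**Day 6 chamber diet.** The plan sets "intake for the day (four meals total) will be equivalent to 80% of the weight maintaining diet to" "account for the restricted physical activity in the confined environment of the chamber". The session is described as eucaloric, at 24°C.

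**Day 7.** On leaving that chamber the same outcome hormones are drawn again, without estradiol and progesterone. The stated purpose is to assess for "stability after a day of energy balance spent inside the metabolic chamber". Data Analysis neither uses this sample as a comparator nor says what follows if hormones are not stable.

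**Intervention samples.** Day 15 (after the 19°C fixed-diet session) and Day 22 (after the fasting session) carry the same instruction: "Upon exiting the chamber, the subjects will complete the VAS. Fasting blood will be then" collected for the full panel. Energy intake in the Day 14 cold session "during this chamber will equal the EE expended during the chamber assessment done on Day 6". In the Day 21 session no food is given.

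**Pre-entry samples on Days 14 and 21.** The text says "blood will be collected for measurement of plasma glucose and insulin" only. Table 4 lists the full hormone panel on those days as well. The two must be reconciled.

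**The concern.** The planned contrast is post-chamber minus pre-chamber. A subject who sat in the chamber for about 23 hours at 24°C in energy balance, with neither cold nor fasting, might still show a hormone change by this measure. Any such change would be credited to the intervention.

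The plan avoids this problem elsewhere. Cold-induced thermogenesis is the Day 14 chamber value minus the Day 6 chamber value. Core and skin temperature changes are taken from measures made during energy balance, which Table 4 places in the Day 6 chamber. In-chamber intake at 19°C is compared with in-chamber intake at 24°C, and the Day 10 text gives shared confinement as the reason. Hormones alone are compared across settings, although a matched sample exists.

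At stake is the cold part of Secondary Hypothesis 5. It predicts directional changes in eleven blood hormones (seven up, four down), and secondary analyses are tested at 0.05 each. A chamber-day shift would bias each affected test by the amount of that shift. It could produce a false effect or, in the opposite direction, hide a true one.

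**Working it through.** **1. What each contrast contains.** Write C for the effect of a 24°C chamber day relative to a floor day (confinement, low activity, chamber diet in place of floor diet), I for the intervention effect, and P for drift over calendar time.

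| Contrast | Contains |
|---|---|
| Day 15 − Day 6 (planned) | I(cold) + C + P over 9 nominal days |
| Day 15 − Day 7 | I(cold) + P over 8 nominal days + any intake difference between the Day 6 and Day 14 sessions |
| Day 22 − Day 6 (planned) | I(fasting) + confinement part of C + P over 16 nominal days |
| Day 22 − Day 7 | I(fasting) + P over 15 nominal days |
| Day 7 − Day 6 | C |

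For fasting, absence of food belongs to the intervention, so only confinement is misattributed. Day 7 removes what the chamber sessions share. It leaves P almost unchanged.

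**2. The plan's own figure.** Data Analysis claims more than 80% power with 68 subjects and alpha 0.05 for a leptin change of −1.8 ± 6.0 ng/mL. Assume that 6.0 is the SD of the paired difference.

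- d = 1.8/6.0 = 0.30; noncentrality = 0.30 × √68 = 2.47; 67 degrees of freedom.
- Two-sided (critical t 1.996): power 0.684.
- One-sided (critical t 1.668): power 0.789.

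The figure is thus approached only with a one-sided test. That is a separate matter and does not depend on the comparator: with the same mean and SD, power is the same against Day 6 or Day 7. The step is shown because the same inputs are used next.

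**3. Illustrative bias.** The documents give no Day 6 to Day 7 shift, so a range is assumed. Set I(cold) = 0 and P = 0, with the same n and SD, a two-sided paired t-test at 0.05, and noncentrality = (shift/6.0) × √68.

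| Assumed shift (ng/mL) | Noncentrality | Rejection rate against Day 6 |
|---|---|---|
| 0 | 0 | 0.050 |
| 0.3 | 0.41 | 0.069 |
| 0.6 | 0.82 | 0.128 |
| 0.9 | 1.24 | 0.230 |
| 1.2 | 1.65 | 0.369 |

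Against Day 7 the rate stays at 0.05 if both chamber sessions carry the same shift.

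**4. Correlation and mediation models.** If every subject has the same C, the change score is (I + constant). The constant goes into the intercept, and correlations and slopes within an intervention do not move. If C differs between subjects, it adds noise to the change score, and it can bias slopes if it is related to the EE or intake response. The documents give no information on that variation.

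**The case against.** The strongest defence is that the plan has seen the issue. Day 7 exists to check stability after a chamber day, the 80% diet is meant to hold energy balance there, and hormones are secondary outcomes or potential mediators. If hormones are stable from Day 6 to Day 7, the choice hardly matters. All this is fair, and it limits the importance of the point. But no rule is attached to the check: an unstable hormone would still be tested against Day 6.

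It is also true that Day 7 is not a perfect match. Day 6 intake is a fixed 80% of the floor diet, whereas Day 14 intake equals the EE measured on Day 6, so any gap between the two remains in Day 15 minus Day 7. Period effects remain as well. Neither limit favours Day 6, which shares the period problem and adds the chamber day.

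A reader might infer more than the documents support:

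- *That reduced feeding is wrongly counted as a fasting effect.* It is not; having no food is the fasting intervention.
- *That the chamber diet is a 20% energy deficit, to be set against the 5–15% rise in EE expected with cold.* The reduction is there to offset restricted activity. Scaling the fasting leptin change (0.20 × 1.8 = 0.36 ng/mL) treats intended energy balance as partial starvation and is not an estimate. Even at 0.36 the illustrative rejection rate is only 0.078.
- *That the mediation analyses are invalid.* A shift common to all subjects leaves them unchanged.
- *That the Day 6 sample is disturbed by an OGTT the day before.* The Admission section allows tasks before the first chamber session in any order.

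**Conclusion.** The point holds for the paired tests of hormone change. The named comparator differs from the intervention samples by a chamber day as well as by the intervention, and a better-matched sample is collected but not used for this purpose.

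Size and direction are unknown because no Day 6 to Day 7 shift is given. The range of about 0.07 to 0.37 for the false-positive rate rests on assumed shifts of 0.3 to 1.2 ng/mL, an assumed SD of the difference of 6.0 ng/mL, 68 complete pairs and no true cold effect. It shows how sensitive the test is; it does not predict a result. Correlation and mediation results are at risk only through between-subject variation in the chamber-day response. The primary EE–intake association does not use this comparator. The change is worth making because it costs little, not because the study's main conclusion depends on it.

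**What to change.** In the hormone paragraph of Data Analysis:

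1. Name the Day 7 post-chamber sample as the comparator for Day 15 and Day 22 changes in the outcome hormones.
2. Use the same change scores in the correlation, mixed and mediation models.
3. Report Day 6 to Day 7 as the chamber-day change, with its mean and between-subject SD. This also gives the stability check a defined output.
4. Keep Day 6 as a sensitivity comparator. Estradiol and progesterone are not drawn on Day 7; Table 4 lists them as descriptive or potential confounders, so the outcome hormones are unaffected.
5. State that Day 7 does not remove period effects or small intake differences between the Day 6 and Day 14 sessions.

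Separately, reconcile Table 4 with the Day 14 and Day 21 text on which hormones are drawn before entry. Those samples, if taken, are also pre-entry and would not replace Day 7.

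The cost is a few sentences. No new draw, visit or assay is needed, since the Day 7 panel is already collected.

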204 intervention and the effect will persist for at least 24 hours.

205 2. The effect of increasing EE by cool temperature exposure on *ad libitum* food intake will be

206 evident both on the day of the intervention and the following day.

207 **Secondary Hypotheses**

208 1. Thirty-six hours of fasting will induce compensatory overeating when the subject is re-

209 introduced to food, and the decrease in 24-h EE during fasting will positively predict the

210 degree of energy consumption.

211 2. The creation of an energy deficit will lead to a decrease in RQ, but the observed changes in

212 energy intake due to changes in EE will be independent of any change in RQ.

213 3. Subjects with less body adiposity will have a greater increase in 24-h EE with cool temperature

214 exposure and a greater decrease in distal skin temperatures while more obese subjects will

215 have a smaller increase in 24-h EE with cool temperature exposure and a greater decrease in

216 proximal skin temperatures indicating greater reliance on insulating mechanisms rather than
217 adaptive thermogenesis.

218 4. Measures of executive function and results of questionnaires related to eating behaviors will
219 be associated with the amount of *ad libitum* caloric intake, but the effects of EE will be
220 independent of these relationships.

221 5. Induced increases in EE will be associated with changes in hormone concentrations, including
222 cold-induced increases in adiponectin, insulin, free T4, TSH, FGF21, glucagon, ghrelin, urinary
223 free cortisol, urinary catecholamines and decreases in leptin, GLP-1, PP and PYY, and at least
224 some of these changes will be associated with the change in food intake.

225 6. The amount of energy intake increase after an increase in EE or the ratio of Δ energy
226 intake/ Δ EE will be directly associated with weight change at 6 months and 1 year.

227 **STUDY DESIGN AND METHODS**

228 **Study Design**

229 This is a inpatient natural history, observational cohort study of healthy human research
230 volunteers with research interventions designed to understand the relationship between the
231 physiologic sensing of EE and food intake behavior. This is primarily a cross-sectional study but with a
232 longitudinal component to assess the association of baseline measurements with future weight
233 change.

234 **Subjects**

235 Sixty-eight healthy participants of all body sizes representing both genders, without evidence

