747 This sample size provides a similar power to detect a correlation of -0.30 at an alpha of 0.05 between
748 the decrease in any of the hormones and cold induced thermogenesis or the expected increase in
749 energy intake. Hormonal changes will be evaluated as possible contributors to the altered 24-h EE
750 and subsequent energy intake first in correlation analyses stratified by type of intervention (i.e., cold
751 exposure and 24-h fasting) and then using similar mixed models as described above. Additionally,
752 behavioral and cognitive test scores will be evaluated as possible predictors of the EE-energy intake
753 link, again using correlations and mixed models. The minimum expected correlation detectable in 68
754 subjects for any of the scores with changes in energy intake will equal 0.30, as reported above.
755 Differences in core body temperature and skin temperatures from measures during energy balance
756 will be calculated for fasting and cold exposure. The significance of these changes will be assessed
757 using one-sample t-tests. The association between these changes and percent body fat as well as EE
758 responses will be assessed using correlation coefficients as above, and again, the minimum detectable
759 correlation with 68 subjects equals 0.30. Significant associations will be evaluated further with mixed
760 models to account for repeated measures, sex, race and age and other potential confounders.
761 Associations between EE responses to each intervention and absolute weight change at each
762 follow-up visit will be quantified by regression models accounting for age, sex, race, and baseline

763 weight. All longitudinal analyses for future weight change will be confirmed using percent change in
764 weight as the dependent variable instead of absolute weight change. Similar models will be calculated
765 for the absolute changes in fat mass and fat free mass including baseline measures as covariates. In
766 case of significant associations between the EE responses to different intervention and weight
767 change, full regression models will be calculated to determine independence of the identified
768 predictors. Mixed model analysis will be used to evaluate the predictive effect of baseline EE
769 measures in relation to the body weight trajectory including all the follow-up visits and accounting for
770 repeated measures. The Compound Symmetry (CR) and the AR(1) covariance structures will be

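### The paired tests of blood-hormone change after cold and after fasting compare a chamber-exit sample with a chamber-entry sample, although a matched 24°C exit sample is already drawn

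*Combined protocol and SAP*

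**What the plan says.** Data Analysis sets one comparator for the hormone changes. They are to be "compared to the baseline fasting concentrations drawn prior to the energy balanced 24-h EE" assessment, by paired t-test or Wilcoxon test. Baseline Phase, Day 6, identifies that sample as the fasting panel taken before the participant enters the 24°C chamber.

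The post-cold panel is taken on Day 15, on leaving the 19°C chamber, when blood is "collected for measurement of insulin, glucagon, leptin, adiponectin, ghrelin, IGF-1, active GLP-1, PP" and the remaining hormones. The post-fasting panel is taken in the same way on Day 22.

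A panel is also taken on Day 7, on leaving the 24°C chamber. Its stated purpose is to check "stability after a day of energy balance spent inside the metabolic chamber". Table 4 lists Day 7 among the hormone time points, as a secondary outcome and potential mediator. The paired-test sentence does not mention it.

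Secondary hypothesis 5 is directional. It expects "cold-induced increases in adiponectin, insulin, free T4, TSH, FGF21, glucagon, ghrelin, urinary" free cortisol and urinary catecholamines, and decreases in leptin, GLP-1, PP and PYY. Secondary outcomes are tested at 0.05 per comparison.

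**The concern.** Day 6 blood follows ordinary days on the ward. Day 15 blood follows about 23 hours of sedentary confinement on a chamber diet at 19°C. The difference is therefore the cold effect plus any chamber-day effect. A chamber-day shift in the predicted direction would be reported as a cold effect, and a shift the other way could hide a real one. The fasting contrast, Day 22 against Day 6, has the same structure.

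Elsewhere the plan compares chamber with chamber. Cold-induced thermogenesis is the difference between "the 24-h EE at 19°C and 24-h EE at 24°C measured on Day 6". For temperature, the plan calculates "Differences in core body temperature and skin temperatures from measures during energy balance". Blood hormones depart from this pattern with no stated reason.

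**Working it through.** **1. What each contrast contains.** Let C be the cold effect, F the fasting effect, H the effect of a chamber day, and D the drift over the stay.
- Planned: Day 15 − Day 6 = C + H + D, and Day 22 − Day 6 = F + H + D.
- Exit against exit: Day 15 − Day 7 = C + D, and Day 22 − Day 7 = F + D, provided H is the same in both chamber stays.

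The change of comparator removes H. It shortens the nominal gap for cold only from 9 days to 8, so D remains.

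**2. Is Day 7 usable?** Hypothesis 5 names 11 blood hormones: 7 expected to rise (adiponectin, insulin, free T4, TSH, FGF21, glucagon, ghrelin) and 4 to fall (leptin, GLP-1, PP, PYY). All 11 are in the Day 7 panel. Estradiol and progesterone are not, but hypothesis 5 does not name them.

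**3. How close is the match?** On Day 6 the food "intake for the day (four meals total) will be equivalent to 80% of the weight maintaining diet to" allow for restricted activity. On Day 14 the energy provided "during this chamber will equal the EE expended during the chamber assessment done on Day 6". These two intakes may differ slightly. The ad libitum days from Day 7 up to the later draw number 4 before Day 15 in the order shown (Days 7–10), 5 if the ad libitum cold session comes first, and 6 before Day 22 (Days 7–10, 15 and 18).

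**4. The plan's own power figure.** For leptin the plan gives −1.8 ± 6.0 ng/mL, n = 68, alpha 0.05 and power above 80%. The standardised change is 1.8/6.0 = 0.30, so the noncentrality is 0.30 × √68 = 2.47 with 67 df. Two-sided power is 0.68 by noncentral t. One-sided power is 0.79 by noncentral t and about 0.80 by the normal approximation. The stated figure is thus reproduced, approximately, only as a one-sided test. That is a separate matter. Two-sided tests are used below.

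**5. Sensitivity to a chamber-day shift.** The documents give no size for H, so these shifts are assumptions. Let d = H/(SD of the paired change), with noncentrality d × √68, C = 0 and D = 0.

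| Assumed d | Leptin equivalent (d × 6.0 ng/mL) | Two-sided rejection rate |
|---|---|---|
| 0 | 0 | 0.050 |
| 0.05 | 0.3 | 0.069 |
| 0.10 | 0.6 | 0.128 |
| 0.15 | 0.9 | 0.230 |
| 0.20 | 1.2 | 0.369 |

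The rate reaches 0.10 at d = 0.08. With a true change of −1.8 ng/mL, a chamber-day shift of +0.6 leaves −1.2 and power falls from 0.68 to 0.37. A shift of −0.6 gives −2.4 and power rises to 0.90.

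**6. Correlation and mediation models.** Adding a constant to every hormone change leaves r and the regression slopes unchanged, and so the Sobel test too. A shift common to all participants therefore does no harm there. If H varies between participants, the false correlation under the Day 6 baseline is k × ρ, where k is SD(H)/SD(hormone change) and ρ is the correlation of H with the EE change. Assumed values give 0.3 × 0.3 = 0.09 and 0.5 × 0.5 = 0.25.

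A Day 7 baseline carries its own risk. The cold EE change is EE on Day 14 minus EE on Day 6, and Day 7 blood is drawn at the end of that same Day 6 session. If a deviation specific to that session loads 0.3, or 0.5, on both change scores, the false correlation is again 0.09, or 0.25, with Day 7 and zero with Day 6. The plan is sized to detect 0.30 in these analyses. The documents do not show which mechanism is larger.

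**7. Double difference.** (Day 15 − Day 14) − (Day 7 − Day 6) removes H and reduces D. With equal, independent errors in the four draws, its variance is twice that of a single difference. A change of 0.30 SD then becomes 0.30/√2 = 0.21, the noncentrality is 1.75, and two-sided power falls from 0.68 to 0.41.

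**The case against.** The best defence is that the plan anticipates the question. Day 7 is drawn to check stability after a chamber day, and the 80% diet is meant to offset restricted activity. If Day 7 equals Day 6, the two comparators agree. That is fair, and the harm may be nil. But the plan states no test or rule for the stability check and does not link it to the cold or fasting contrast. If H is zero, the Day 7 contrast loses nothing so long as the SD of change is similar.

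A reader might infer that Day 7 has no role beyond a stability check. Table 4 does not support that, because it lists Day 7 as a secondary-outcome and mediator time point. Data Analysis also adds mixed models for hormonal changes without saying which draws enter. The gap lies in the paired-test sentence.

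A reader might also infer that the correlation and mediation models should move to Day 7. Steps 6 of the working shows why not: a common shift leaves them unchanged, and Day 7 shares a session with the EE baseline.

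Finally, Table 4 places the hormone panel on Days 14 and 21 as well, whereas the Intervention Phase text for those days specifies glucose and insulin only. If Table 4 is right, the double difference is available for all 11 hormones. If the text is right, it is available for insulin alone. Either way, Days 14 and 21 are entry samples, and the analysis text still names the energy-balance baseline.

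**Conclusion.** The point holds for the paired mean-change tests of blood hormones: the mean-change part of secondary hypothesis 5 and the parallel fasting test. The planned comparator leaves any chamber-day effect inside the estimate, and a better-matched sample is already collected.

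The size is unknown. It would be tempting to read the rates of 7% to 37% as the trial's expected false-positive rate. They are not, because the documents establish neither the existence, the direction nor the size of a chamber-day shift. The rates assume no true cold effect, no drift, n = 68 and two-sided tests. The claim that Day 7 removes the shift assumes that a chamber day acts alike at both stays.

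Urinary cortisol and catecholamines are 24-hour collections tied to the chamber sessions and are not affected. Neither is the primary EE–intake analysis. Severity is minor: a cheap improvement.

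**What to change.** First settle whether the full panel or only glucose and insulin is drawn on Days 14 and 21, and align Table 4 with the Intervention Phase text.

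Then replace the comparator sentence in Data Analysis, for the paired mean-change tests of blood hormones only, with wording such as: *The effect of cold will be tested as Day 15 minus Day 7 and the effect of fasting as Day 22 minus Day 7. Day 7 minus Day 6 will be reported as the effect of a 24°C chamber day. Comparisons with Day 6 will be sensitivity analyses.*

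Keep the Day 6 baseline in the correlation and mediation models. A Day 7 version can be a sensitivity analysis.

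State that drift over the stay and a possible small difference in chamber intake remain. For hormones drawn before and after both chambers, (Day 15 − Day 14) − (Day 7 − Day 6) can be added as a sensitivity analysis, with the matching contrast for Days 22 and 21. The loss of precision should be acknowledged.

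The cost is a few sentences. The main change needs no new draw, so the admission blood total stays at 32 + 151 + 76 + 60 + 60 = 379 mL.
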